**Inclusion/Exclusion Criteria**

Name the subject group/sub sample

Adult OCD subjects

Create or insert table to describe the inclusion criteria and methods to ascertain them

Inclusion criteria	
CRITERION	METHOD OF ASCERTAINMENT
1) Patient must be 18-60 years of age at the time of	Clinical Interview

consent	
2) Patient must be physically healthy and, if female, must be non-pregnant. Females of childbearing potential must comply with contraceptive restrictions noted in the protocol.	Clinical interview and physical examination (including EKG and blood and urine tests) by trained M.D, and as part of screening.
3) Patient must fulfill DSM-5 criteria for OCD, OCD being the principal disorder (i.e., currently the most severe and needing of treatment) and have had OCD for at least one year	Clinical Interview by trained M.D. or Ph.D. and results of SCID
4) Patient with a Y-BOCS score of greater than or equal to 16 prior to entering trial.	Clinical interview and assessment by trained rater
5) Patient is off all psychotropic (except selective SRIs) and other types of drugs likely to interact with nabilone (e.g., antihistamines or anticholinergic drugs). Patients taking a selective SRI must be on a stable dose for 6 weeks prior to study entry. Note: Subjects on clomipramine will be excluded because both clomipramine and nabilone can cause orthostatic hypotension.	Clinical interview
6) Each patient must have a level of understanding sufficient to provide written informed consent to all required study tests and procedures.	Clinical interview
7) Subject must be able to tolerate a treatment-free period	Clinical Interview

Create or insert table to describe the exclusion criteria and methods to ascertain them

Exclusion criteria	
1) History of violence.	Psychiatric evaluation
2) Presence of psychotic symptoms or lifetime history of schizophrenia, bipolar disorder, substance-induced psychotic disorder, or psychosis due to a general medical condition.	Psychiatric evaluation/SCID
3) Presence of developmental disorder or intellectual disability.	Clinical interview
4) Severely depressed patients with HAMD-17 (17-item Hamilton Depression Rating Scale) >25 or judged clinically to be at risk of suicide.	Clinical Interview/SCID and HAMD-17
5) OCD patients with primary symptoms of hoarding	SCID/Y-BOCS check-list
6) Female patients who are either pregnant or nursing.	Clinical interview, medical exam, and blood pregnancy test

7) Patients planning to commence EX/RP during the period of the study or currently in EX/RP treatment.	Clinical interview
8) Current substance use disorders (meeting criteria within the past year, with the exception of nicotine) or positive urine toxicology at screening, or any adverse reaction to a cannabinoid (e.g., panic attack with THC use).	Clinical interview and urine toxicology.
9) History of any significant medical condition (e.g., hypotension) that might increase the risk of participation given the known side effects of nabilone.	Clinical interview and medical examination

**Waiver of Consent/Authorization**

Indicate if you are requesting any of the following consent waivers  
 Waiver of consent for use of records that include protected health information (a HIPAA waiver of Authorization)

- No
- Waiver or alteration of consent
- No
- Waiver of documentation of consent
- No
- Waiver of parental consent
- No

**Consent Procedures**

Is eligibility screening for this study conducted under a different IRB protocol?

Yes  
 Indicate NYSPI IRB #  
 6112R

Describe Study Consent Procedures

A member of the clinic (MD psychiatrist) will meet with prospective subjects to discuss the study. The staff member will review the consent form and answer any questions.

Indicate which of the following are employed as a part of screening or main study consent procedures

- Consent Form

## Study Procedures

Describe the procedures required for this study

Screening/initial evaluation

Patients deemed eligible following screening (by phone or in person) will undergo with their consent: 1) an evaluation by a senior clinician (M.D. or Ph.D.); 2) a Structured Clinical Interview for DSM-5; 3) a Y-BOCS to assess OCD severity; and 4) a medical evaluation (i.e., history, physical, routine blood tests [including blood pregnancy test for females], urine toxicology, and EKG). Those who meet entry criteria will provide written informed consent.

Randomization and Treatment Intervention

After the baseline evaluation, participants will be randomized to one of two groups. Randomized assignments (stratified by SSRI use) will be generated using a random number generator in SPSS.

Group 1 (n=10) will receive nabilone at 1 mg BID over 4 weeks. (Note: These patients will be offered EX/RP at no cost in open treatment after the 4 weeks of the trial).

Group 2 (n=10) will receive nabilone at 1 mg BID plus therapist-guided EX/RP (as described below) during 4 weeks.

All subjects will meet weekly with a study psychiatrist to receive nabilone and to review side effects.

Those randomized to EX/RP will also meet with a study therapist (MA or PhD-level) to receive 9 sessions of EX/RP (i.e., a treatment planning session plus 8 sessions of EX/RP) over four weeks according to a treatment manual. Following standard procedures, EX/RP will include therapist-aided exposure, self-guided exposure as homework, ritual prevention, and education about relapse prevention.

Assessments (independent evaluator)

An independent evaluator (Master's level or above) who is not involved with study treatment will assess global psychopathology (CGI); OCD symptoms (YBOCS); sensory phenomenon (Sao Paulo Sensory Phenomena Scale), depressive symptoms (HAM-D) **and at follow-up, any changes in treatment since study end and adherence to EX/RP lifestyle**. Subjects will also complete self-reports that assess depression and anxiety (DASS) and quality of life (Q-LES-Q). Subjects will be evaluated at weeks 0, 1, 2, 3, and 4 and also 1 month after study end (week 8, by phone or in person).

You can upload charts or diagrams if any

## Criteria for Early Discontinuation

### Criteria for Early Discontinuation

Participants are free to withdraw from the study at any time for any reason. Study doctors are to discontinue patients from the study if patients:

- Request early discontinuation or withdraw consent.
- Experience a serious or intolerable adverse event that prevents the patient from continuing.
- In the Investigator's opinion, are experiencing a clinically significant deterioration in OCD (i.e., YBOCS score six points greater than their baseline at any time point).
- In the Investigator's opinion, are experiencing a clinically significant deterioration in a comorbid condition such as major depression. For example, if a patient became suicidal or their symptoms of depression increased such that the depressive symptoms were much or very much worse relative to baseline and the HDRS-17 is no longer <25, they would be discontinued from the study.
- Commit a protocol violation, including lack of compliance.
- Are "lost to follow-up."
- Encounter other conditions (such as administrative issues or pregnancy).

If a patient discontinues from the study at any time at their own request or at the study doctor's discretion, the reason(s) for discontinuation are to be recorded by the study. Subjects will be asked to return to the study site for final safety assessments as scheduled for the final study visit. Patients withdrawing from the study for reasons related to the study medication (usually adverse events) will be followed until the event(s) have resolved or no further action is required.

## Blood and other Biological Samples

Please create or insert a table describing the proposed collection of blood or other biological specimens  
N/A

## Assessment Instruments

Create a table or give a brief description of the instruments that will be used for assessment

- Structured Clinical Interview for DSM-5 (SCID, 1-2 hours) The SCID is a semi-structured clinician rated instrument that assesses the major adult Axis I disorders in DSM-5
- Yale-Brown Obsessive Compulsive Scale (Y-BOCS, 45 minutes) This is a semi-structured clinician rated instrument used to measure obsessions and compulsions separately over five separate dimensions (time consumed, distress, interference, degree of resistance, control). This is the gold-standard measure of OCD

symptoms.

- Clinical Global Impression (CGI, 1 minute). This is a clinician rated instrument for rating global psychopathological severity.
- 17-Item Hamilton Depression Rating Scale (HDRS-17, 5 minutes). This is a clinician rated instrument for rating depression.
- Sao Paulo Sensory Phenomena Scale (SPSPS, 6 minutes). This is a clinician rated instrument for rating sensory phenomena associated with OCD.
- Depression Anxiety Stress Scales (DASS, 5 minutes): 21-item self-report measure that assesses depression, anxiety, and stress experienced in the past week.
- Quality of Life Enjoyment and Satisfaction Measure (Q-LES-Q, 4 minutes): Self-report questionnaire that assesses subjects' satisfaction and enjoyment in daily life.
- PhenX Toolkit Hand Dominance Measure: This measure assesses one's handedness, and is based off of the Edinburgh Handedness Inventory (2 minutes)
- Intolerance of Uncertainty Scale: 27-item self-report questionnaire that assesses a person's ability to tolerate uncertainty. (4 minutes)
- Spielberger State-Trait Anxiety Inventory (STAI): 40 item self-report questions that assesses state and trait anxiety (6 minutes)
- Patient EX/RP Adherence Scale (PEAS, 5 minutes): This 3-item scale is used by a therapist to assess subject adherence to EX/RP homework and targets the quantity and quality of exposures and the degree of ritual prevention.
- Side Effect Checklist (SECL, 3 minutes): Side Effect Assessment: possible side effects will be rated on a scale from 0 (none) to 3 (severe). Weight, blood pressure and heart rate will be assessed at each visit.

Please attach copies, unless standard instruments are used

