- History of any significant medical condition that may increase the risk of participation

Interventions

Intervention Name (use generic name if established): Nabilone

Intervention Type: Drug

Intervention Description (do not repeat information already included in arm/group descriptions): Nabilone is a synthetic form of THC and cannabinoid 1 receptor agonist. It acts on the brain's "endocannabinoid system," which has been hypothesized to play a role in OCD.

Intervention Name: Exposure and Response Prevention Therapy

Intervention Type: Behavioral

Intervention Description: Exposure and Response Prevention Therapy (EX/RP) is a type of Cognitive-Behavioral Therapy for OCD that involves intentionally confronting situations that trigger obsessional distress while refraining from doing compulsions.

Outcome Measures

Primary Outcome Measure 1: Feasibility of recruitment of patients with OCD into a study of nabilone

Time Frame: Total participants who consent to participate for the duration of the study

Safety Issue (Is this outcome measure assessing a safety issue?): No

Primary Outcome Measure 2: Tolerability of nabilone (e.g. adverse events reported)

Time Frame: Baseline (Week 0), Week 1, Week 2, Week 3, Week 4

Safety Issue (Is this outcome measure assessing a safety issue?): Yes

Primary Outcome Measure 3: Yale-Brown Obsessive-Compulsive Scale (YBOCS)

Time Frame: Weeks 0 and 4

Safety Issue (Is this outcome measure assessing a safety issue?): No

Secondary Outcome Measures: Hamilton Depression Rating Scale, 17-Item (HDRS-17)

Time Frame: Weeks 0 and 4

Safety Issue?: No

Statistical Analysis Plan

For both the YBOCS and HDRS-17 measures, we will calculate change scores for the nabilone and nabilone+EX/RP groups based on the difference between Baseline (Week 0) and Week 4. This preliminary study is not designed to assess for statistical differences between groups, and thus only the overall magnitude of change between groups will be compared. We will assess feasibility of recruitment based on the total number of participants enrolled over the duration of the study. Finally, we will assess nabilone's tolerability in OCD based on weekly self-reporting of side effects using a checklist drawn from the nabilone package insert, and any other adverse events that occur over the course of the study.

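### The protocol names orthostatic hypotension as a nabilone effect, but specifies no postural blood pressure reading, and the SAP plans no summary of the vital signs collected

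*Protocol*

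**What the plan says.** **Entry.** Inclusion criterion 5 of the protocol (Inclusion/Exclusion Criteria) states: "Subjects on clomipramine will be excluded because both clomipramine and nabilone can cause orthostatic hypotension". Exclusion criterion 9 rules out "History of any significant medical condition (e.g., hypotension) that might increase the risk of participation given the known side effects of nabilone".

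**On treatment.** Under Assessment Instruments, the Side Effect Checklist entry adds: "Weight, blood pressure and heart rate will be assessed at each visit". Posture, number of readings and timing relative to dose are not stated. Study Procedures says: "All subjects will meet weekly with a study psychiatrist to receive nabilone and to review side effects". The list of risk-minimising procedures also has study physicians and an independent evaluator monitoring participants each week.

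**Risk text.** The Risks section refers to the package insert, lists the commonest reactions and gives an incidence table from placebo-controlled studies. Neither the list nor the table includes hypotension.

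**Analysis.** Primary Outcome Measure 2 in the SAP is tolerability, at Weeks 0 to 4. The Statistical Analysis Plan paragraph bases it on "weekly self-reporting of side effects using a checklist drawn from the nabilone package insert, and any other adverse events" arising during the study. The SAP does not mention blood pressure or heart rate.

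**The concern.** Orthostatic hypotension is a fall in pressure on standing. Readings taken in one posture do not show it, and the protocol does not ask for two. A site could follow the text exactly and collect no postural data. Whatever blood pressure and heart rate values are collected then have no planned place in the results.

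This matters because tolerability is the pilot's stated goal and one of its primary outcomes, and the data are meant to support later grant applications. Both arms receive nabilone open label, so a symptom report cannot be attributed to the drug by comparing arms. Objective within-person readings would help a later team judge whether symptoms went with a fall in pressure. They would also show falls that produced no symptoms. Without them, a statement that nabilone was well tolerated would rest on symptoms and on whatever was recorded as an adverse event.

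**Working it through.** The documents contain no figure for this risk, so there is nothing to reproduce. The main check is to follow the named risk from entry to analysis.

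**Step 1. Is the risk named?** Yes. Inclusion criterion 5 attributes it to nabilone as well as to clomipramine. Exclusion criterion 9 links hypotension to nabilone's known side effects.

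**Step 2. Is a matching measurement specified?** Only in part. Blood pressure and heart rate are taken at each visit, but no resting and standing pair is described.

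**Step 3. Does the analysis use it?** No. The SAP names two inputs to tolerability, the checklist and adverse events, and no vital-sign summary.

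**Step 4. What can still reach the results?**

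| Event | Route into the tolerability results |
|---|---|
| Postural fall with symptoms | Checklist, weekly psychiatrist review, adverse event report |
| Low reading noticed at a visit | Only if someone records it as an adverse event |
| Postural fall without symptoms | No specified route |

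**Step 5. Illustrative size.** Inputs:
- n = 20 completers (protocol, Description of Subject Population), all on nabilone.
- True rate p: 5%, 10% or 20%. This is assumed, because the documents give none.
- Share of cases detected s: 1, 0.5 or 0.25. This is also assumed.

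The chance of at least one detected case is 1 − (1 − p·s)^20.

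| s | p = 5% | p = 10% | p = 20% |
|---|---|---|---|
| 1 | 64% | 88% | 99% |
| 0.5 | 40% | 64% | 88% |
| 0.25 | 22% | 40% | 64% |

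For example, with p = 10% and s = 0.25, 1 − (1 − 0.025)^20 = 0.397.

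**Step 6. What would a report of no cases mean?** With 0 of 20 detected, the one-sided 95% upper bound on the detected rate p·s is 1 − 0.05^(1/20) = 13.9%. With full detection this is also the bound on p. If s is known to be 0.5, the bound on p is 13.9/0.5 = 27.8%. If s is 0.25, it is 13.9/0.25 = 55.6%. A clean result therefore excludes much less when detection is partial, and the plan gives no basis for judging s.

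**The case against.** The strongest reply is that the trial does monitor this risk. Blood pressure is taken at every visit, a psychiatrist reviews side effects weekly, and participants who withdraw for medication-related reasons are followed until the event resolves. The SAP's adverse event input is open-ended, and Primary Outcome Measure 2 gives adverse events only as an example. This stands. A reader might infer that the named risk cannot be detected, or is not measured at all during dosing. The documents do not support either reading.

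Three other tempting inferences also fail:
- That only one reading is taken per visit. The text does not give the number.
- That the checklist has no item for hypotension or light-headedness on standing. Its items are not shown, and it is drawn from the package insert.
- That the 52% vertigo rate in the risk table measures the problem. Vertigo is a different event, and the rate comes from other studies.

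It can also be said that the entry criteria already reduce the risk, that the clomipramine exclusion concerns two drugs together, and that the risk list and table do not claim to be exhaustive. These points are fair. They weaken any charge of contradiction, but they do not supply a postural reading or an analysis of the vital signs.

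Finally, every participant receives nabilone, so change from Week 0 has no drug-free comparator. This also stands, and it limits the remedy to description.

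**Conclusion.** The concern holds in a limited form. The protocol names orthostatic hypotension as a nabilone effect and acts on it at entry. It specifies no postural measurement on treatment, and the SAP plans no summary of the blood pressure and heart rate it collects. Detection therefore relies on symptoms and on ad hoc adverse event recording. Asymptomatic postural falls may be missed, and good tolerability could be reported without objective data on this risk.

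The gap is moderate and cheap to close; it does not undermine the pilot. Its size cannot be taken from the documents. The calculations show only how incomplete detection weakens a finding of no cases, under assumed rates, assumed detection shares and 20 independent participants. The conclusion also assumes that no separate procedure outside these documents already prescribes postural readings.

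**What to change.** 1. **Protocol, Assessment Instruments.** Specify blood pressure and heart rate at rest and again after standing, at Week 0 before the first dose and at Weeks 1 to 4. Record the time since the last dose at each on-treatment visit. The documents do not describe the drug's time course, so this is recorded to help interpret the readings.
2. **SAP, Primary Outcome Measure 2.** Add a supporting descriptive summary, by arm and overall, of within-person change from Week 0 in resting values and in the standing-minus-resting difference, with the number of participants measured at each week. Make no hypothesis test, in keeping with the SAP's statement that the study is not built for group comparisons.
3. **Protocol, Risks section.** Reconcile the risk list and table with the eligibility text on hypotension. Check whether the checklist already has a relevant item before changing it.

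**Cost.** A few minutes at each existing visit, with the same staff and equipment. For 20 completers this is 20 × 5 = 100 paired readings over Weeks 0 to 4, plus a short SAP addition. With no drug-free comparator, the changes can be described but not attributed to nabilone.

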### Off label and investigational use of drugs/devices

Choose from the following that will be applicable to your study

✓ Drug

Select the number of drugs used in this study

1

#### Drug #1

Name of the drug

Nabilone

Manufacturer and other information

Nabilone is a synthetic cannabinoid that is FDA-approved for the treatment of chemotherapy-induced nausea and vomiting and has also been used as an adjunct therapy for chronic pain management. It acts on the brain's endocannabinoid system and is similar to tetrahydrocannabinol (THC), the primary psychoactive compound found naturally in Cannabis (or marijuana). Thus, nabilone is a controlled substance, and it may produce subjective effects in some that are similar to a marijuana-like "high."

Approval Status

No IND is required

Choose one of the following options

FDA conditions are met (see 'Rules')

Explain

The protocol meets FDA's rules for waiver of IND. These rules include:

1. The study drug is lawfully marketed in the United States;
2. The study is not intended to be reported to the FDA as a well-controlled study in support of a new indication or use; or support any significant change in the drug's labeling;
3. The study is not intended to support a significant change in the advertising for a prescribed drug;
4. The study does not involve a change in route of administration, dosage level, patient population, or other factors that significantly increases the risks associated with use of the drug product;
5. The study complies with IRB evaluation and informed consent requirements; and
6. The study sponsor and/or investigator do not represent in a promotional context that the drug is safe and effective for the purposes in which it is under investigation.

**Research Related Delay to Treatment**

Will research procedures result in a delay to treatment?

Yes

Maximum duration of delay to any treatment

Half of the patients will receive an evidence-based treatment (EX/RP) from the outset. The other half will be offered EX/RP after the trial termination and therefore the maximum time from the time of consent to beginning EX/RP for this group will be 8 4 weeks. [name] and her clinical team will be in contact with the OCD patients every week from the time of signing consent for this study throughout the study to evaluate their ability to continue in the protocol. If a patient suddenly meets any exclusion criteria (e.g., active suicidal ideation) or no longer met the inclusion criteria of being "able to tolerate a treatment-free period," the patient would be removed from the study and referred for treatment. Patients may refuse to participate at any point and seek outside treatment.

Maximum duration of delay to standard care or treatment of known efficacy

Same as above.

Treatment to be provided at the end of the study

Upon completion of the trial, participants in group 1 (medication only) will be offered the same EX/RP treatment received by participants in group 2 (medication plus EX/RP).

**Clinical Treatment Alternatives**

Clinical treatment alternatives

Subjects do not have to participate in this study to receive treatment for OCD. There are two evidence-based

first-line treatments for OCD. The first is a class of medications called Serotonin Reuptake Inhibitors (SRIs). The second is EX/RP. Subjects will have these treatment options explained to them by the study doctor, and they will be offered the option to receive outside referrals for one or both of these treatments rather than participating in the study.

